10.4.2 Analysis of the Secondary Endpoint(s)

Kaplan-Meier curve will be used to estimate the PFS and OS for *RELA*-fusion and non *RELA*-fusion recurrent ependymoma with 2 or less prior chemotherapies, and *RELA*-fusion and non *RELA*-fusion recurrent ependymoma with more than 2 prior chemotherapies. Logrank test and proportional hazard model will be used to compare the PFS between *RELA*-fusion and non *RELA*-fusion recurrent ependymoma. Safety will be assessed by reporting the grades of toxicity and the type of toxicity observed for all patients and summarizing data using the descriptive statistics, including mean, standard deviation and confidence intervals.

Received MDASI-BT or SP forms will be checked versus the timing schedule and considered as valid if they fall within ten days of the scheduled assessment. Compliance rates will be calculated as the number of received valid forms over the number of expected forms. Differences between groups in compliance will be tested by use of Fisher's exact test at every time point.

We will use descriptive statistics to describe how patients rate symptom severity and interference with function at each time point. Error bar graphs for each of the symptoms will be constructed at each time point. The proportion of patients rating their symptoms to be 7 or greater (on a 0-10 scale) will also be reported. We will construct individual patient profiles for each of the selected symptoms to describe the individual patients' patterns of change over time. We will calculate the mean core symptom severity, mean severity of the MDASI-BT or SP and mean symptom interference at the time of clinical evaluation. Estimates of differences in the mean symptom severity and mean symptom interference between responders and non-responders will be estimated in the intent to treat population. All patients with at least one valid questionnaire will be included in the analyses. In addition to the descriptive statistics, linear mixed model will be used to further study the trajectory of longitudinally evaluated patient reported outcome measures, where random intercepts will be used to capture the within-subject correlation.

Differences of at least 2 points will be classified as the minimum clinically meaningful change in the symptom severity and symptom interference measures. For example, an increase of 2 points or more would mean a moderate improvement, whereas a decrease of 2 points or more would be interpreted as moderate worsening. For individual symptoms, a rise in a symptom score means deterioration, whereas a reduced score means improvement of the specific symptom.

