2.4 BASELINE EVALUATION

Tests done at screening do not need to be repeated at baseline if performed in designated time frame prior to start of study drug.

Within 14 days prior to first dose:

- MRI of the head and/or spine with gadolinium as specified in [Appendix B](#).
- Archived tumor samples will be collected to do molecular studies as described in Section [5.3](#). If the patient has previously been on another study at NIH, and the required molecular profiling has been done, then additional pathology material may not be needed (any time prior to treatment initiation).
- The MDASI-BT and/or MDASI-SP . The choice of instrument will be based on the location of the index lesion for study enrollment. This may be in the brain (MDASI-BT), spine (MDASI-SP) or both (completing both instruments if lesions in the brain and spine are being followed for response). (For English speaking subjects only).
- Research blood for SNP Studies (See section [5.1.2](#))
- Research blood for Pharmacogenomic Studies (Cohort 1 only) (See section [5.1.2](#))
- Concomitant Medications
- Adverse events
- EKG (within 3 days prior to first dose)
- Subjects will complete and sign an NIH advanced directives form which is mandatory on this study.

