3.4 QUESTIONNAIRES

The MDASI-BT and/or MDASI-SP will be administered at baseline and at the time of imaging analysis. Every attempt should be made to administer the MDASI-BT and/or MDASI-SP prior to informing the patients about the results of the imaging study. The MDASI-BT or MDASI-SP will be completed only by the patient, unless changes in vision or weakness make this difficult. If this occurs, then the caregiver or research assistant may read the questions to the patient or assist with marking the severity number or score as described by the patient.

The average time to complete these instruments is 5 minutes. Only for English speaking patients.

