3.6 STUDY CALENDAR

Procedure	Screening	Baseline ¹	Cycles 1-24 (28 \pm 3 days) ¹			28 Days FU ¹¹	Long Term FU ^{10,11}	
			Days ¹				with PD	without PD
			1	8	15			
Marizomib ²			X	X	X			
NIH Advance Directives Form ³		X						
Medical History	X							
Confirmation of Pathology	X							
Height	X							
Physical exam, neurological exam, KPS	X		X			X	X	
Weight	X		X	X ¹²	X ¹²			
Vital signs	X		X ⁴	X ⁴	X ⁴	X	X	
EKG	X	X	X ¹³	X ¹³	X ¹³			
CBC with differential	X		X ⁵	X ⁵	X ⁵	X		
Biochemical profile ⁶	X		X ⁵	X ⁵	X ⁵	X		
Amylase / lipase/CK/ GGT, LDH			X ⁵			X		
Urinalysis	X							
Serum or urine pregnancy test ⁷	X		X ⁵					
PT, INR, aPTT, fibrinogen			X			X		

Procedure	Screening	Baseline ¹	Cycles 1-24 (28+/-3 days) ¹			28 Days FU ¹¹	Long Term FU ^{10,11}	
			Days ¹				with PD	without PD
			1	8	15			
Tumor evaluation (MRI) ⁸	X	X	X			X		X
Concomitant Medications (See 6.1)		X	X	X	X	X		X
Adverse events (See 6.1)		X	X	X	X	X		X
Research blood for SNP Studies		X						
Research blood for Pharmacogenomic Studies (Cohort 1 only)		X						
Collection of archival tumor sample for research studies		X						
MDASI-BT and/or MDASI- S ⁹		X	X			X		X
Phone call or e-mail for survival/new cancer treatments							X	X

¹ Tests done at screening or baseline do not need to be repeated on baseline or Day 1 of Cycle 1 if performed in designated time frame prior to start of study drug. Time window +/- 3 days is allowed for Days 1, 8 and 15.

² 0.8 mg/m² IV.

³ All subjects will complete and sign an NIH advanced directives form which is mandatory on this study.

⁴ See section 3.2 for vital signs schedule on days of drug infusion.

⁵ Labs will be obtained within 72 hours prior to dosing

⁶ Biochemical profile: electrolytes, BUN, creatinine, AST, ALT, total bilirubin, calcium, phosphorus, albumin, magnesium, uric acid

⁷ For women of child-bearing potential only

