⁸ MRI head and/or spine with gadolinium at screening/baseline and every 8 weeks after beginning of treatment. Confirmatory scans should also be obtained in 4-8 weeks period of time following initial documentation of objective response. Patients with prior therapy that included interstitial brachytherapy or stereotactic radiosurgery must have confirmation of true progressive disease at screening rather than radiation necrosis based upon either PET or Thallium scanning, MR spectroscopy, or surgical/pathological documentation of recurrent disease. After initial confirmation of progressive disease at screening, these patients will be evaluated during treatment with regular MRI.

⁹ At baseline and then within 14 days prior to each imaging study.

¹⁰ All SAEs ongoing at the 28-Day Safety Follow-up visit must be monitored and followed up by the Investigator until stabilization or until the outcome is known, unless the subject is documented as “lost to follow-up.” Subjects with PD after the 28-Day Safety Follow-up visit, will be followed every 6 months (± 1 month) for survival (including assessment of any further anticancer therapy) by phone call or e-mail.

Subjects without PD at the 28-Day Safety Follow-up visit should continue follow up visits and tumor imaging by MRI per schedule in the Section **3.5.2**

¹¹ If subjects are unable or not willing to come to NIH to for follow up visits, they will be followed by phone call or e-mail for survival, adverse events (for 1 year only) and further tumor therapy.

¹² If significant (> 3 kg) weight loss or gain is observed during a cycle.

¹³ Within 2 hours after study drug infusion and additionally any time if clinically indicated.

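### A questionnaire completed 11 to 14 days before imaging is allowed by the study calendar but can be classed as invalid by the ten-day rule in section 10.4.2

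*Combined protocol and SAP*

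**What the plan says.** Four sections bear on when a questionnaire should be completed and when it counts.

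- **Section 3.6, footnote 9 (collection):** "At baseline and then within 14 days prior to each imaging study". Footnote 8 of the same calendar sets the imaging schedule: "MRI head and/or spine with gadolinium at screening/baseline and every 8 weeks after beginning of treatment".
- **Section 2.4 (baseline collection):** the MDASI is among the items listed under "Within 14 days prior to first dose".
- **Section 3.4 (administration):** the instrument "will be administered at baseline and at the time of imaging analysis", with no window in days, and preferably before the patient learns the scan result.
- **Section 10.4.2 (analysis):** "Received MDASI-BT or SP forms will be checked versus the timing schedule". The test applied in that check is a ten-day limit, under which forms are "considered as valid if they fall within ten days of the scheduled assessment".

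Section 10.4.2 gives validity two uses. The first is compliance: "Compliance rates will be calculated as the number of received valid forms over the number of expected forms", with a Fisher's exact test between groups at each time point. The second is inclusion: a patient needs at least one valid questionnaire to enter the analyses.

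**The concern.** The collection window is 14 days and the validity window is ten. Where both are counted back from the same date, a patient can do what the calendar allows and still be recorded as non-compliant. The compliance rate would then partly measure when within the permitted window forms were completed, not whether they were completed. A difference in timing between groups could appear in the Fisher's exact test as a difference in compliance. A patient whose only form fell on days 11 to 14 would also fail the inclusion rule. Longitudinal patient-reported outcomes are a stated secondary objective (section 1.1.2), and the compliance rate is what a reader would use to judge how complete those data are.

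**Working it through.** The plan gives no figure to reproduce here. The check compares the two windows day by day.

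**Inputs**
- Permitted on-study completion days, counted back from imaging: 0 to 14, which is 14 − 0 + 1 = 15 days (section 3.6, footnote 9).
- Validity limit: at most 10 days from the reference date (section 10.4.2).
- Visit tolerance: "Time window +/- 3 days is allowed for Days 1, 8 and 15" (section 3.6, footnote 1). Applying it to the MRI date is an assumption, used only in reading 2.

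**Rule.** A form completed *d* days before the actual scan is invalid if its distance from the reference date exceeds 10.

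**Reading 1: the reference is the actual imaging date.** The distance is *d*. Days 0 to 10 pass (11 days) and days 11 to 14 fail: 15 − 11 = 4 days, and 4/15 = 26.7% of the permitted days.

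**Reading 2: the reference is the nominal 8-week date.**
- Scan 3 days early: the distance is *d* + 3, which exceeds 10 when *d* ≥ 8. Days 8 to 14 fail, 7 of 15.
- Scan on the nominal date: 4 of 15, as in reading 1.
- Scan 3 days late: the distance is *d* − 3 for the early forms, which exceeds 10 only when *d* = 14. That is 1 of 15.

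**Reading 3: the reference is the questionnaire's own 14-day window.** Every permitted day lies inside it, so 0 of 15 fail.

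**Which reading fits.** Section 3.4 ties the questionnaire to imaging, and footnote 9 counts days back from imaging. Imaging is therefore the anchor that the protocol itself uses, which favours reading 1. No section states reading 3.

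**Baseline.** If the reference is the first dose, the same count applies: days 11 to 14 before first dose are permitted by section 2.4 and fail the ten-day rule. If the reference is the baseline visit itself, which has its own calendar column separate from Cycle 1 Day 1, there is no conflict.

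**After alignment.** With validity running from 14 days before the scan to 10 days after it, 0 of the 15 permitted days fail. On the 8-week (56-day) schedule, the 10 days after one scan and the 14 days before the next add to 24 days, fewer than 56, so a form could not be valid for two consecutive scans.

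**The case against.** The strongest reply is that the conflict hangs on an undefined term. Under reading 3 no permitted form fails, and an analysis window tighter than the collection window is not in itself an error. The first part stands as a limit on certainty: the conflict is conditional on the reference date. It does not remove the point, because the reading that escapes the conflict is written nowhere and the reading that sections 3.4 and 3.6 support produces it. A deliberately tighter window is possible, but the plan gives no reason for one, and it would still be wrong to report forms that followed the calendar as non-compliance.

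Three stronger readings are tempting and are not supported.

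- **That invalid forms are discarded.** Section 10.4.2 takes them out of the compliance numerator and does not let them satisfy the inclusion rule. It does not say that they leave the symptom summaries, the individual profiles or the mixed model. Nor does it specify a change-from-baseline estimator, so loss of every later comparison for a patient with an invalid baseline form does not follow.
- **That about 27% of on-schedule forms would fail, so that perfect compliance would be reported as about 73% (11/15).** This needs completion days to be spread evenly over the window. Section 3.4 places the questionnaire at the time of imaging, and the calendar puts the MDASI and MRI in the same columns. Both point to completion near the scan.
- **That the baseline form is certainly affected.** Its separate calendar column makes this the weaker part.

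**Conclusion.** The two windows conflict if the scheduled assessment is the imaging date, which is the natural reading but not a stated one. On that reading 4 of the 15 permitted days give a form that follows the protocol and is classed as invalid. If the nominal 8-week date is meant and the three-day tolerance covers the MRI, the range is 1 to 7 of 15. These are counts of days. The documents give no distribution of completion days, so the share of forms cannot be calculated and may be near zero. The baseline form is affected only if its reference is the first dose.

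The stated consequences are an understated compliance rate, a between-group compliance test that can pick up timing, and possible exclusion of a patient with no other valid form. All of this concerns a mainly descriptive secondary outcome. The primary endpoint, PFS6, and the rules for stages 1 and 2 do not depend on it. The change is worth making because the rule as written can give a wrong compliance figure and the correction is small.

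**What to change.** In section 10.4.2:

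1. Name the reference date: the imaging date for on-study forms and the first dose for the baseline form.
2. Count a form as valid if it was completed within 14 days before that date. For on-study forms, keep the present ten-day allowance after the scan. A window that only looked backwards would newly invalidate forms completed shortly after the scan, which the current two-sided rule accepts when measured from imaging.
3. Use this one window for both the compliance numerator and the inclusion rule.

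Then align the timing wording of sections 2.4, 3.4 and 3.6 with it. While section 10.4.2 is open, a sentence on whether forms outside the window enter the summaries and the mixed model would remove the remaining ambiguity.

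The cost is a small wording change, with no new data collection. The downside is that some valid forms will be slightly further from the scan, which the calendar already permits.

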6.3.3 RANO Disease Response Criteria

For the purposes of this study, patients should be re-evaluated for response every 8 weeks. Confirmatory scans should also be obtained in 4-8 weeks period of time following initial documentation of objective response.

Table 6: RANO Criteria for Response

RANO Criteria for Response (28)	CR	PR	SD	PD
T1 gadolinium enhancing disease	None	≥ 50% ↓	< 50% ↓ but < 25% ↑	≥ 25% ↑ ¹
T2/FLAIR	Stable or ↓	Stable or ↓	Stable or ↓	↑ ¹
New lesion	None	None	None	Present ¹
Corticosteroids	None	Stable or ↓	Stable or ↓	n/a [†]
Clinical status	Stable or ↑	Stable or ↑	Stable or ↑	↓ ¹
Requirement for response	All	All	All	Any ¹

RANO Criteria for Response (28)				
	CR	PR	SD	PD

¹ Progression occurs when this criterion is present
 
† Increase in corticosteroids alone will not be taken into account in determining progression in the absence of persistent clinical deterioration.
 
↓ = decreased, ↑ = increased,
 
CR = complete response, PR = partial response, SD = stable disease, PD = progressive disease. If PD is unclear based on white matter changes, patients may be kept on trial.
 
FLAIR, fluid-attenuated inversion recovery; NA, not applicable.
				

Stable/No Progression (SD): No evidence of new measurable lesions on MR imaging. The designation of Stable/No Progression requires a minimum of 12 weeks duration. All measurable and evaluable sites must be assessed using the same techniques as baseline.

Partial response (PR): ≥ 50% reduction in the sum of products of all measurable lesions over baseline sum observed using the same techniques as baseline. The patient must be on a stable or decreased dose of corticosteroids to be evaluable for response.

Complete response (CR): Complete resolution of all lesions. The patient cannot be on any corticosteroids with the exception of adrenal replacement doses.

Progression (PD): 25% increase in the sum of products of all measurable lesions over smallest sum observed (over baseline if no decrease) using the same techniques as baseline, OR clear worsening of any evaluable disease, OR appearance of any new lesion/site, OR failure to return for evaluation due to death or deteriorating condition (unless clearly unrelated to this cancer).

Unknown: Progression has not been documented and one or more measurable or evaluable sites have not been assessed.

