6.3.4 Evaluation of Best Overall Response

The best overall response is the best response recorded from the start of treatment until disease progression/recurrence (taking as reference for progressive disease the smallest measurements recorded since the treatment started). The patient’s best response assignment will depend on the achievement of both measurement and confirmation criteria.

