10.3 POPULATIONS FOR ANALYSIS

Evaluable for objective response: Only those patients who have measurable disease present at baseline, have received at least one cycle of therapy, and have had their disease re-evaluated will be considered evaluable for response. These patients will have their response classified according to the Section **6.3.3**. (Note: Patients who exhibit objective disease progression prior to the end of cycle 1 will also be considered evaluable.)

Evaluable for toxicity: All patients will be evaluable for toxicity from the time of their first treatment with Marizomib.

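### Section 10.4.2 compares MDASI means by response, a post-baseline grouping, with no landmark or time-varying status, so the contrast can favour responders even if response has no effect on symptoms

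*Combined protocol and SAP*

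**What the plan says.** Section 10.4.2 calculates mean severity and "mean symptom interference at the time of clinical evaluation", and then says that differences "between responders and non-responders will be estimated in the intent to treat population". It does not define responder.

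The only patient-level response summary is in section 6.3.4: "The best overall response is the best response recorded from the start of treatment until disease progression/recurrence". That summary also depends on confirmation. Under section 6.3.3, "patients should be re-evaluated for response every 8 weeks", with a confirmatory scan 4 to 8 weeks after first documentation. The study calendar (section 3.6) has the MDASI completed within 14 days before each scan.

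The longitudinal analysis is a linear mixed model "where random intercepts will be used to capture the within-subject correlation". No response term is stated.

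Section 10.3 defines no intent-to-treat set. It limits response evaluability to patients with measurable disease who "have received at least one cycle of therapy, and have had their disease re-evaluated will be considered evaluable for response", plus those with objective progression before the end of cycle 1. Section 10.4.2 separately includes all patients with at least one valid questionnaire.

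**The concern.** The two groups are formed by something that happens after baseline. A patient who progresses at the first scan can only be a non-responder. A confirmed responder has, by definition, stayed progression free long enough to respond and be confirmed. If MDASI scores rise around progression, those raised scores collect in one group.

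Section 1.2.6 wants to know whether any benefit comes with better or worse symptoms. A contrast tilted towards responders could be read as evidence of symptom benefit when it partly reflects who was able to be classed as a responder.

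Table 6 adds a second route. Complete or partial response requires stable or improved clinical status and sets limits on steroid use, so responder status depends partly on how the patient is doing.

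The population wording is a separate gap. Patients not evaluable for response have no responder status, and no rule assigns them one.

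**Working it through.** The plan gives no response rate, MDASI standard deviation or precision target for this contrast, so there is no figure to reproduce. The check asks what the contrast shows when response has no effect on symptoms.

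**Inputs from the documents.** Scans and forms every 8 weeks (6.3.3, 3.6); confirmation, taken here as the next scan; PFS6 of 0.30 or 0.60 (10.1); 50 patients (10.2).

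**Assumed inputs.** Exponential PFS; baseline score mean 3, SD 2; visit noise SD 1; individual slope SD 0.25 per visit; radiographic shrinkage probability 0.2 or 0.4, independent of symptoms; scores rising by d = 0, 1 or 2 points at progression; no form after the progression scan. The clinical-status condition is either off or on; when on, a response requires no rise of 2 or more points from baseline. There are 400,000 simulated patients per scenario.

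**Quantity.** D(k) = mean score of ever-responders at visit k minus mean score of all other patients with a form at visit k. Negative values favour responders.

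**Hand check at week 8, clinical-status condition off.** No eventual confirmed responder has progressed by week 8, so D = -d × P(progressed by week 8) / P(never a responder). Eight weeks is 56/30.44 = 1.84 months.
- PFS6 0.30: P(progressed) = 1 - 0.30^(1.84/6) = 0.31. With 13.8% ever-responders (shrinkage probability 0.4), D = -d × 0.31/0.862 = -0.36d. Simulation: -0.36 for d = 1 and -0.72 for d = 2.
- PFS6 0.60: P(progressed) = 1 - 0.60^(1.84/6) = 0.145. With 12.6% ever-responders (shrinkage probability 0.2), D = -d × 0.145/0.874 = -0.17d. Simulation: -0.17 and -0.34.

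**Simulated false differences, grouping by ever-response**

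| Assumption | Raw means, weeks 8 to 24 | Change from baseline, week 24 |
|---|---|---|
| No rise, no clinical-status condition | within 0.03 of zero | within 0.01 of zero |
| Rise of 1 to 2 points at progression | -0.12 to -0.77 | -0.11 to -0.48 |
| Clinical-status condition only | -0.03 to -0.16 | -0.29 to -0.36 |
| Both | -0.21 to -0.87 | -0.40 to -0.83 |

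If scores instead rise by 1 to 2 points before progression, the false difference at weeks 8 to 24 is about 0.06 to 1.1 points in favour of responders.

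**Sampling error.** SE = SD × √(1/n1 + 1/n2), with 50 patients, assumed SD 1.5 to 2.5 and response rates of 10% to 30%.
- Smallest: 1.5 × √(1/15 + 1/35) = 0.46.
- Largest: 2.5 × √(1/5 + 1/45) = 1.18.

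Fifty is the full enrolment. If the trial stops after stage 1 there are 18 patients, and the MDASI is given to English speakers only.

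**Effect of a week-16 landmark.** Using only response documented by week 16, the progression-driven difference falls to about 0.00 to 0.03. If the label for week 16 is allowed to depend on a confirming scan at week 24, part of the artefact returns: -0.08 to -0.33 in change from baseline. With the clinical-status condition, a landmark does not clear the difference. Up to about 0.23 remains in one set of assumptions. In the version with late confirmation, 0.33 to 0.38 remains with the condition alone and 0.41 to 0.70 with both mechanisms.

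**The case against.** The strongest reply is that the text does not commit to the harmful version. A reader might infer that eventual responders are compared at every visit. Neither part of that is written. The time-point wording belongs to the description of all patients: "We will use descriptive statistics to describe how patients rate symptom severity and interference with function at each time point". Objective status is recorded at each evaluation (6.3.1) and forms are completed shortly before scans, so near-concurrent response status is a possible reading, and under it much of the problem falls away. This stands as a limit on how firmly the plan can be characterised. It does not dispose of the point. Best overall response is the only patient-level summary defined, and section 10.4.5 uses the same responder and non-responder wording for baseline tissue features, which needs one fixed label per patient.

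Second, a reader might infer that a false benefit is bound to appear. It is not: the first row of the table is about zero. Section 6.3 itself notes that tumour can grow in some CNS regions without immediate signs. Against that, Table 6 counts clinical worsening as progression, and section 6.3.3 counts failure to return because of deterioration, so some link between symptoms and progression is built in.

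Third, the contrast is one secondary estimate alongside visit-by-visit descriptions, individual profiles and a mixed model. Section 1.2.6 asks about symptoms alongside a survival benefit rather than objective response. That stands. It would be wrong to say that the symptom objective cannot be met.

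**Conclusion.** The point holds in a limited form. On its most natural reading, the plan groups patients by a post-baseline outcome in a way that can tilt the MDASI contrast towards responders without any effect of response.

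The illustrated size is about 0.1 to 1.1 points. It rests on assumed score distributions, response rates, exponential PFS and a rise in symptoms around progression, so it shows direction and order of magnitude only. It is below the plan's own threshold ("Differences of at least 2 points will be classified as the minimum clinically meaningful change") and comparable with the standard error at 50 patients. A single result could therefore not separate it from a real association.

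Two stronger conclusions might be inferred, and the documents support neither. The efficacy decisions are unaffected, because they rest on PFS6 counts and this contrast has no test or decision rule. Nor does a landmark make the comparison clean, because clinical status and steroid use remain inside the response definition.

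**What to change.** In section 10.4.2, define responder and the time at which status is fixed, then use one of two analyses.
- **Landmark.** Take patients who are progression free and under follow-up at a fixed scan, for example week 16. Classify them by response documented up to that scan, and compare later MDASI scores adjusted for baseline. State whether confirmation is required. If it is, the confirming scan must also fall by the landmark.
- **Time-dependent status.** Enter response to date, as known when the form is completed, as a covariate in the planned mixed model, with baseline adjustment.

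For the landmark analysis, replace the intent-to-treat wording with the landmark set restricted to patients with a valid questionnaire. State that clinical status and steroid use are part of the response definition, and report the result as an association only.

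This changes SAP wording and needs no new data. The cost is precision. Sixteen weeks is 112/30.44 = 3.68 months, so with exponential PFS the share progression free is 0.30^(3.68/6) = 0.48 or 0.60^(3.68/6) = 0.73. That is about 24 or 37 of 50 patients. With the same SD and response share, the standard error grows by a factor of 1/√0.48 = 1.4 or 1/√0.73 = 1.2.

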The MDASI-BT and/or MDASI-SP consists of symptoms rated on an 11-point scale (0 to 10) to indicate the presence and severity of the symptom, with 0 being “not present” and 10 being “as bad as you can imagine.” Each symptom is rated at its worst in the last 24 hours. Symptoms included on the instrument include those commonly associated with cancer therapies, and those associated with the underlying disease. The questionnaire also includes ratings of how much symptoms interfered with different aspects of a patient's life in the last 24 hours. These interference items include: general activity, mood, work (includes both work outside the home and housework), relations with other people, walking, and enjoyment of life. The interference items are also measured on 0 - 10 scales.

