- Progression-free survival at 12 months of *RELA*-fusion and non *RELA*-fusion recurrent ependymoma patients with with more than 2 prior chemotherapies treated with marizomib (Cohorts 2 and 4) will be assessed as proportion of patients that are progression-free at 12 months timepoint after initiation of treatment
- Median progression-free survival (PFS) of *RELA*-fusion and non *RELA*-fusion recurrent ependymoma patients with with more than 2 prior chemotherapies treated with marizomib (Cohorts 2 and 4) will be assessed as median amount of time subject survives after initiation of therapy

- Overall survival (OS) of *RELA*-fusion and non *RELA*-fusion recurrent ependymoma patients with with more than 2 prior chemotherapies treated with marizomib (Cohorts 2 and 4) will be assessed as median amount of time subject survives after initiation of therapy
- Objective response to marizomib in *RELA*-fusion and non *RELA*-fusion recurrent ependymoma patients with with more than 2 prior chemotherapies treated with marizomib (Cohorts 2 and 4) will be assessed using RANO Criteria for Response **6.3.3**.
- Safety of marizomib in recurrent ependymoma patients and in a subset of patients with more than 2 prior chemotherapies (Cohorts 2 and 4) will be scored using CTCAE version 5.0.
- Outcome measures using self-reported symptom severity and interference with daily activities using the MDASI-BT and/or MDASI-SP instrument.

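### The example in section 10.4.2 reverses the direction of the 2-point meaningful change in MDASI severity and interference, calling a rise an improvement although higher scores are worse

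*Combined protocol and SAP*

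**What the plan says.** Patient-reported symptoms are a secondary objective (section 1.1.2) and a secondary endpoint (section 10.1.2): "Outcome measures using self-reported symptom severity and interference with daily activities", measured with the MDASI-BT, the MDASI-SP or both.

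Section 1.2.6 describes the scale. Each symptom is rated on 11 points "to indicate the presence and severity of the symptom, with 0 being" absence of the symptom and 10 the worst the patient can imagine. Six interference items (general activity, mood, work, relations with others, walking, enjoyment of life) are also rated 0 to 10 for how much symptoms interfered. No verbal anchors are given for these.

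Section 10.4.2 forms the summaries as "mean core symptom severity, mean severity of the MDASI-BT or SP and mean symptom interference". It also plans a high-score summary: "The proportion of patients rating their symptoms to be 7 or greater (on a 0-10 scale) will also be reported".

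The same section then gives the interpretation rule in three steps:

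- Threshold: "Differences of at least 2 points will be classified as the minimum clinically meaningful change in the symptom severity and symptom interference measures". No direction is stated here.
- Example: "an increase of 2 points or more would mean a moderate improvement, whereas a decrease of 2 points or more" is to be taken as worsening; in full, the second half reads "a decrease of 2 points or more would be interpreted as moderate worsening".
- Individual items: "For individual symptoms, a rise in a symptom score means deterioration", and a fall means improvement.

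**The concern.** The example and the sentence after it give opposite directions for scores built from the same items. The correct direction is stated only for individual symptoms. For the severity means and for interference, the reversed example is the only direction that section 10.4.2 states. A reader could take the two sentences as two deliberate conventions, one for items and one for summaries.

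Section 1.2.6 gives the reason for collecting these data: to learn whether any survival benefit comes with better symptoms, or whether worse symptoms offset it. The direction of the label decides how that question is answered. Worsening is a realistic outcome here: section 1.2.5.1 reports treatment-emergent headache in 25-53% of patients in the glioblastoma studies of this agent. If the example is followed, a meaningful rise in mean severity or interference is described as benefit and a meaningful fall as harm.

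**Working it through.** The plan gives no figure to reproduce. The check compares the scale with the stated directions and then runs assumed scores through the plan's own rules.

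**Step 1: direction of the items.** For severity, the anchors in section 1.2.6 are 0 = absent and 10 = worst imaginable, so higher is worse. For interference, the items rate how much symptoms interfered, on 0 to 10. Higher is worse by inference from that wording, because no anchors are given.

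**Step 2: direction of the summaries.** Section 10.4.2 uses means. Sections 1.2.6, 3.4 and 10.4.2 mention no reverse scoring. With mean = (sum of item scores) / k for k items, the mean moves the same way as its items. The 7-or-greater summary agrees with this, since it singles out high scores.

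**Step 3: is there a scale that runs the other way?** The MDASI-BT and MDASI-SP are the only patient-reported instruments in the plan, and their summaries are severity and interference. No functioning or quality-of-life score, on which a rise would be good, is planned.

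**Step 4: assumed scores.** These illustrate the rule and do not estimate how often it would bite.

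| Assumed change | Mean before | Mean after | Change | Label from the example |
|---|---|---|---|---|
| All k symptom items 5 to 7 | 5k/k = 5.0 | 7k/k = 7.0 | +2.0 | moderate improvement |
| All k symptom items 7 to 5 | 7k/k = 7.0 | 5k/k = 5.0 | -2.0 | moderate worsening |
| Six interference items 3 to 5 | (6 × 3)/6 = 3.0 | (6 × 5)/6 = 5.0 | +2.0 | moderate improvement |

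In the first row every item is a deterioration under the individual-symptom sentence, and every item moves from below 7 into the 7-or-greater group. The mean is nevertheless labelled improved. In the second row every item improves and leaves that group, and the mean is labelled worse. An unreversed mean cannot improve when all its components deteriorate, so the example contradicts both the scale and the sentence that follows it.

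**Step 5: after correction.** With the two words exchanged, rows 1 and 3 become moderate worsening and row 2 becomes moderate improvement. No computed value changes.

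**The case against.** The strongest case on the other side concerns weight. The sentence is an illustration, not the definition of an endpoint or test. The planned outputs (means, the 7-or-greater proportion, individual profiles, mixed-model estimates) are the same either way. No output counts patients who improved or worsened by 2 points; the responder comparison in section 10.4.2 uses responder status as a grouping variable, not as a product of this rule. For severity, a careful analyst can recover the right direction from the anchors and the individual-symptom sentence. On this view it is a minor drafting slip.

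Most of this is right, and it limits the consequence to labels. It does not remove the point. The plan says differences of this size will be classified, so the direction governs how a secondary endpoint is described. For interference, section 10.4.2 contains no correct statement to fall back on. Correcting the direction after the data have been seen would also be a departure from the written plan, which is easily avoided now.

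A second objection is that the interference half rests on inference, because no anchors are given. That is true, and that half is less firmly documented than the severity half. A rating of how much symptoms interfered still has only one natural direction.

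Reading the example as a rule for composites and the next sentence as a rule for items does not reconcile them, because the composites are means of those items.

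**Conclusion.** The concern holds. The example is reversed for symptom severity on the plan's own anchors, and for interference on the plain sense of what the items rate. The conclusion assumes that the means are taken over unreversed items, as the documents imply by stating no reversal.

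The effect is confined to the labels attached to changes of 2 points or more. How many patients or comparisons would be mislabelled cannot be computed, because no such count is specified. The PFS6 endpoint, the stage rules and the sample size are unaffected. It should be fixed because, followed as written, it inverts the clinical reading of a secondary endpoint.

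**What to change.** In the example sentence of section 10.4.2, exchange *increase* and *decrease*, so that a fall of 2 points or more is a moderate improvement and a rise of 2 points or more is a moderate worsening. Leave the 2-point threshold sentence and the individual-symptom sentence unchanged; the three will then agree with each other and with section 1.2.6.

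The cost is two words in one sentence. No new data are needed and no analysis changes.
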